## Minimizing risks from the fMRI

*Exclusion of individuals with contra-indications for scanning*: Individuals at primary risk for the exposure to high magnetic fields due to the presence of potentially dangerous ferrous materials in the body are excluded. This eliminates the risk of attractive forces or thermal heating. Participants are told of these exclusions during recruitment and must complete a comprehensive screen of any potential metal on their body. This screening form is reviewed by a member of the team with level 2 training, and it is confirmed by the scanner operator before the participant is allowed in the scanner room. For participants who possess orthopedic screws or pins that are firmly in bone, participants can only be scanned if the type of screw or pin is considered safe according to the *Reference Manual for Magnetic Resonance Safety. Implants and Devices, 2020 Edition* Participants are withdrawn from the study if it is determined there is any contra-indication for scanning.

Avoidance of other risks from the high magnetic field: The MRI suite is coded in terms of zones. The entire scanner suite has controlled access, and only individuals with appropriate training (see staff training) are allowed to permit people into the scanner control room or MRI and only after they have been screened. Subjects are reminded to remove any jewelry before entering the scanner room and are screened with a handheld metal detector before entering the scanner room. Subjects are given a box/locker to place their wallet, keys and other personal belongings before entering the scanner room. All study personnel have undergone safety training and must adhere to safety rules to limit potential risks in the scanner suite.

Even if a participant passes screening for the presence of ferrous implants or tattoos, participants with orthopedic hardware are told to squeeze a ball so that they can be removed from the scanner in the unlikely event that they feel sensations such as warming at the site of an orthopedic screw or tattoo.

Avoidance of claustrophobia: Participants are excluded if they report a history of claustrophobia, and they are warned in advance that the space is cramped and that they will have a head coil placed around their head. If an individual does become claustrophobic during the scan, they can inform the study staff and discontinue the study at any time. Subjects will be given a ball to squeeze so that they can stop the scan at any time.

Avoidance of physical discomfort from lying in the scanner: Individuals with a history of chronic or recent acute back pain are excluded from the study. Subjects are warned that they will need to lie on their back in a still position for up to 90 minutes. Pillows and cushions are used to keep the subject comfortable and the scan operator always checks that the person is comfortable before closing the scan room door. If the subject does need to move during the scan, they can be repositioned as long as it is done between scans.

Avoidance of discomfort from volume of the scanner: Subjects are given earplugs and noise reducing headphones to limit the volume of the scanner.

*Incidental Findings:* If an incidental finding is observed during a scan, it will not be initially shown to the subject. After scanning, the scan data will be electronically submitted to the University Radiology Group imaging server, where it will be read by a neuroradiologist who will provide a brief written report. If the neuroradiologist determines the scan has clinical significance that warrants attention, the PI will inform the participant and after a release of information form is completed, will provide the imaging data and report to a physician of the participant's choice.

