TESTING AND INTERVENTION. Participants will attend a baseline visit at the Center for Advanced Human Brain Imaging Research (CAHBIR) at Rutgers University, during which functional magnetic resonance imaging (fMRI) coupled with a meal test will be performed to assess peripheral and central feeding pathways (7, 8). fMRI scans will be performed during resting state to assess functional connectivity of feeding related networks, with a specific focus on connectivity between the hypothalamus, insula, anterior cingulate, ventromedial/orbitofrontal prefrontal cortex and amygdala (9, 10). Activation to food (vs non-food) images will be assessed to index responsivity to appetitive feeding networks including the above regions and the ventral striatum using paradigms that have previously been found to be sensitive to trait and state in multiple studies (11-13). Thereafter participants will consume a liquid meal (525 kcal; Ensure Plus, Abbott). fMRI will be repeated immediately after the meal. Participants will attend a second visit at the IFNH, during which laboratory work coupled with a meal test will be performed to assess satiety hormones and inflammatory markers. Fasting blood draw will be taken, and the participants will consume a liquid meal (525 kcal; Ensure Plus, Abbot) followed by blood draws at 30, 60, 120, 180 and 240 min postmeal. Upon completion of baseline testing and providing a fecal sample, participants will consume NBT-NM108 (a mixture of inulin, Fibersol-2, and brans of oat, wheat, corn and sorghum; Notitia Biotechnologies) daily for 4 weeks. At the completion of the 4-week intervention, all sampling and testing will be repeated as per baseline. At baseline and end of intervention, participants will be interviewed with appetite and physical activity questionnaires (Appendix C and G) and requested to complete a 24-h food recall using MyFitnessPal, a mobile health app on their phone.

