## D. Endpoints

[figure not shown]
- 1. Primary Outcome
  - Gut microbiota composition at Weeks 0 and 4
- 2. Secondary outcomes:

- Weeks 0, 1, 2, 3, and 4
  - a. Weight measured in pounds
- Weeks 0 and 4
  - a. Hormones related to satiety and hunger include ghrelin, peptide YY (PYY), leptin, glp-1/GIP, insulin, glucose
  - b. Inflammatory markers include c-reactive protein (CRP), interleukin 6 (IL-6) and tumor necrosis factor-alpha (TNF-), adiponectin
  - c. Outcome of fMRI showing responsivity of appetite feeding networks in the brain
  - d. Caloric intake recorded in MyFitnessPal application
  - e. Appetite behavior measured by hyperphagia questionnaire and visual analog scale (VAS)
  - f. Physical activity measured by physical activity questionnaire

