## 1.8 Specimen Collection

## A. Primary Specimen Collection

## Types of Specimens:

- Stool. Each participant will be provided with kits to collect fecal samples at home in Week 0 and Week 4. The fecal sample collection kit has been cleared by FDA for at-home use. Instructions and supplies will be provided to collect these samples at home (Appendix D).
- 2) Blood. Venous blood draws (10 ml each) will be taken during the baseline and Week 4 post-intervention meal tests (T=0, 30, 60, 120, 180 and 240 min of each test) at IFNH by qualified professionals including phlebotomists, registered nurses and physicians.
- Annotation: Data to be annotated or associated with each specimen will include participant code, age, sex, ethnicity, medical history, and medications.

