- Contraindications for MRI scanning, including Ferrous material implanted in or on the 0 body, including flakes or filings, surgical clips, bullets, or electrical devices such as a pacemaker, or nonremovable ferrous jewelry (fillings in teeth and permanent retainers are permitted). Individuals with surgical pins or plates above the neck are excluded. Surgical pins or plates below the neck are exclusions, except when the material is fixed to bone, and considered acceptable by the Reference Manual for Magnetic Resonance Safety. Implants and Devices, 2020 Edition. Almost all recent orthopedic implants are made of materials that are not ferromagnetic and therefore are safe for scanning, and even though some screws are still made of ferromagnetic materials these are firmly screwed into bone. In cases where the material is unknown or deemed unsafe for scanning by the Reference Manual for Magnetic Resonance Safety. Implants and Devices, the participant will be excluded. History of eye injury involving metallic materials, shavings in eyes, or welding without a face mask. Lead/iron tattoos and tattoos performed by a nonprofessional artist if the pigment material is unknown. Claustrophobia (history of significant anxiety in closed places). Back problem that would prevent the subject from laying still comfortably for up to 60 minutes.

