## 4.3 Number of Subjects

A. Total Number of Subjects

10 patients; 5 male and 5 female

- B. Total Number of Subjects If Multicenter Study N/A
- C. Feasibility

DEEP6 identified 26 patients via EPIC system who had the diagnosis of PWS with only 5 patients meeting our inclusion criteria. For this reason we are expanding our diagnosis coding to include hyperphagia syndrome. Given hyperphagia is a hallmark feature of PWS and the particular behavior we are aiming to study, this expansion should improve our subject pool and allow us to enroll 10 patients.

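### The untimed rule withdrawing anyone with an MRI contraindication from the whole study could cost Week-4 primary-outcome data that need no scanner

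*Combined protocol and SAP*

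**What the plan says.** The withdrawal rule is in section 4.7 E, under the fMRI risks: "Participants are withdrawn from the study if it is determined there is any contra-indication for scanning". It names the study, not the scan, and sets no time limit.

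fMRI is a secondary outcome in section 1.3 D: "Outcome of fMRI showing responsivity of appetite feeding networks in the brain". The primary outcome there is "Gut microbiota composition at Weeks 0 and 4". Section 1.8 A has the stool collected away from any scanner: "Each participant will be provided with kits to collect fecal samples at home in Week 0 and Week 4". Section 1.3 A places the hormone and inflammatory-marker test at a visit separate from the baseline scan: "Participants will attend a second visit at the IFNH, during which laboratory work coupled with a meal test will be performed".

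MRI contraindications are also an entry exclusion in section 4.1 B: "Contraindications for MRI scanning, including Ferrous material implanted in or on the" body, followed by a long list that includes claustrophobia and back problems. Section 1.9 A schedules scanning at Week 0 and again at Week 4. Section 1.3 A starts the product only after baseline testing and repeats all testing after four weeks.

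The target is 10 participants (sections 1.5 and 4.3), with no power calculation.

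**The concern.** A problem with a secondary procedure can end follow-up for the primary outcome. A participant may complete baseline, take the product, and then turn out not to be scannable at Week 4. Applied as written, the rule takes that person out of the study, although the home stool kit, meal test, weight, food recall and questionnaires could all still be done.

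The planned analysis is a Week 0 to Week 4 comparison within person, so a missing Week-4 sample removes that person's change altogether. With 10 participants there is little room for avoidable loss. Recruitment was already tight before the diagnosis was broadened: "DEEP6 identified 26 patients via EPIC system who had the diagnosis of PWS with only 5 patients meeting our inclusion criteria". Section 6.1 defines no analysis set and no rule for incomplete pairs, and no replacement rule is stated.

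**Working it through.** The plan states no power or precision figure, so there is none to reproduce. The check compares the provisions and then illustrates the size of a loss.

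**Can the rule apply after baseline?**
- Section 1.9 A requires the MRI safety form to be reviewed before scanner-room entry. Section 4.7 E adds confirmation by the operator and a metal-detector check before entry.
- Scans take place at both Week 0 and Week 4. The text does not say that a fresh form is completed at Week 4, but repeating the testing as at baseline, with checks tied to scanner-room entry, makes a Week-4 finding possible.
- Several listed contraindications could arise or surface between visits, such as a new implant, a metallic eye injury, a tattoo or a back problem.

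**What does withdrawal entail?**
- Section 4.7 E does not say.
- The protocol spells out the consequence of removal or withdrawal in two other places. Section 4.5 D (dissent or withdrawn surrogate consent) ends testing and the supplement. The hospitalization paragraph of section 4.7 E ends all data and sample collection.
- Both end follow-up, and nothing in the MRI text provides for continued non-MRI collection. The natural reading is that Week-4 collection stops.

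**What is lost?**
- All Week-4 stool, blood, weight, intake and questionnaire data not yet collected.
- The order of stool collection and scan at Week 4 is not fixed. If the stool was already provided, the primary pair survives; otherwise it is lost. One lost pair is 1/10 = 10% of the planned sample.

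**Illustrated size for a paired mean change.** Section 6.1 uses a two-tailed paired t-test where the data are normal. In units of the SD of the change, the 95% confidence interval half-width is t(0.975, n−1)/√n.

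| Pairs | Half-width (SD) | Relative to 10 | Power at change of 1.0 SD |
|---|---|---|---|
| 10 | 0.715 | 1 | 80% |
| 9 | 0.769 | 0.769/0.715 = 1.075 | 75% |
| 8 | 0.836 | 0.836/0.715 = 1.169 | 68% |

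The power column comes from the noncentral t distribution with noncentrality √n × 1.0. The two-sided 5% level and the change of 1.0 SD are assumptions; the documents give neither.

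**How likely is a loss?** The documents give no rate. If each of 10 participants independently had probability p of such a withdrawal, the chance of at least one is 1 − (1 − p)^10. This gives 40% for p = 5%, 65% for p = 10% and 89% for p = 20%. These rates are assumed, only to show the range.

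**The case against.** The strongest reply is that the rule mainly enforces eligibility. It closes a paragraph about excluding people with contraindications, the same conditions are exclusions in section 4.1 B, they are explained at recruitment, and product starts only after a baseline that includes fMRI. A contraindication present at entry should therefore surface before any product is taken. This stands, and it confines the point to findings after baseline.

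It can also be said that wanting participants with both scan and microbiota data is a defensible choice, since the hypothesis concerns central appetite regulation. That supports the entry exclusion. It does not explain giving up the Week-4 primary sample of someone already enrolled and treated.

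The figures can be challenged too. The primary comparison is a PERMANOVA on UniFrac distances, not a paired mean; this is a pilot without a power target; and the figure of 5 eligible among 26 describes the pool before the diagnosis was widened to hyperphagia, which the protocol expects to help. All of this is correct, so the numbers are illustrative.

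Three stronger readings are tempting but unsupported:
- **That data already collected are thrown away.** Nothing says so. The protocol is silent on how such data are handled.
- **That claustrophobia in the scanner forces withdrawal.** The text is permissive: "they can inform the study staff and discontinue the study at any time". The following sentences let the participant stop only the scan.
- **That the rule biases the analysed group by selecting on implants or scanner tolerance.** That selection comes from the entry criteria, which are not in question here.

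**Conclusion.** The point holds in a narrow form. The withdrawal rule in section 4.7 E is broader than eligibility enforcement needs. For a contraindication found or arising after baseline it would, on the natural reading, end collection of Week-4 outcomes that do not depend on MRI, including the primary one. Each case costs one of 10 primary pairs if the Week-4 stool has not yet been provided and the participant is not replaced.

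The interval widening of 7.5% with 9 pairs and 17% with 8 applies to outcomes tested by paired t-test. How often this would happen cannot be judged from the documents, and over a 28-day course it may be rare or never occur. The conclusion rests on reading withdrawal here as it is used for withdrawn consent and hospitalization. If the sponsor meant otherwise, the text needs to say so, and the amendment is the same. This is a cheap improvement, not a flaw that undermines the trial.

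**What to change.** Reconcile sections 4.1 B, 4.7 E and 6.1 with a short amendment:

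- Limit the withdrawal rule to contraindications found before baseline is complete, where it enforces the entry exclusion.
- For participants who have completed baseline and started product, state that inability to be scanned ends MRI procedures only. Consented non-MRI Week-4 outcomes (stool, blood, weight, intake, questionnaires) are still collected.
- In section 6.1, state that data already collected from such participants are analysed, and report the number of fMRI pairs separately from the number of stool pairs.
- Optionally, align the claustrophobia sentence with the one on stopping the scan, keeping the participant's right to leave the study.

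MRI safety screening and the entry exclusions are unchanged. Whether product continues after such a finding is left to the investigator. The cost is a few sentences and the possibility of fewer fMRI pairs than stool pairs.

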## Hospitalization during study

If patients are hospitalized during the study, they will be removed from the study and discontinue all data and sample collection. Subjects will need to contact the study PI, [name], D.O. at [name] if hospitalized during the study.

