## 1.5 Sample Size Justification

No power calculation is performed for this pilot study. We aim to recruit 10 patients with hyperphagia(5 male and 5 female) to capture a reasonable degree of variations in gut microbiota composition.

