## E. Minimizing Risks of Harm

Participants will be provided with oral and written instructions and supplies to collect fecal samples at home without direct physical contact with the specimens throughout the process (Appendix D). The specimens will be stored in a sealed container, a leak-proof secondary package (a sealable plastic bag lined with absorbent pads) and an outer package (e.g. a shipping box). Participants are not required to store the samples at home; they will mail the specimens to the research team using the shipping supplies provided.

To minimize adverse effects due to NBT-NM108, they will also be advised to drink enough fluids throughout the study (approximately eight 8-ounce glasses of fluid a day including the amount of water taken together with NBT-NM108) to avoid constipation. Participants will be asked to monitor potential adverse events daily. If participants report an adverse event, a member of the study team will contact them to ask follow-up questions about the degree of severity (mild, moderate, or severe) and the frequency of the adverse events. The study physician (PI [name]) will assess the adverse events and, if necessary, she will instruct the participants to discontinue treatment.

Measuring fasting blood glucose during the study both involves a finger prick that pierces the skin. There may be a bruise, bleeding, or infection, at the place where the skin is pierced. However, infection is rare. To minimize adverse effects, venipuncture will be done by a certified venupuncturist.

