## 6.3 Data and Safety Monitoring

## A. Data/Safety Monitoring Plan

A Data and Safety Monitoring Board (DSMB) will approve the protocol before the study is initiated, and after 30% of the participants complete 14 days of the intervention to review study progress including recruitment, retention, adherence, adverse events and study outcomes, as well as to ensure that participant safety is addressed adequately. Reports of adverse events will be used to assess the safety of the study.

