## B. Data/Safety Monitoring Board Details

The DSMB will include Rutgers University faculty members with expertise in medicine, epidemiology and/or statistics who are not directly involved with the study. The Board will meet before the study is initiated, and after 30% of the participants complete 14 days of the intervention to review study progress and provide recommendations related to continuing, modifying or terminating the study. Any serious adverse event that is life-threatening or results in death, that is possibly, probably, or related to the research protocol, will trigger an immediate suspension of the research. All details about the DSMB are found in **Appendix F.** 

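### The hospitalisation rule stops all data collection with no stated exception for safety data, which conflicts with the safety monitoring plan in Section 6.3

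*Combined protocol and SAP*

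**What the plan says.** Four parts of the protocol bear on this.

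- **Section 4.7 E, Hospitalization during study.** Of patients hospitalised during the study: "they will be removed from the study and discontinue all data and sample collection". The rule does not distinguish causes of admission or types of data. One link remains: "Subjects will need to contact the study PI".
- **Section 4.7 E, general paragraph on adverse events.** When a participant reports an event, "a member of the study team will contact them to ask follow-up questions about the degree of severity" and about its frequency. The study physician then assesses it.
- **Section 6.3 A.** "Reports of adverse events will be used to assess the safety of the study".
- **Section 6.3 B.** The suspension rule covers "Any serious adverse event that is life-threatening or results in death" and continues: "that is possibly, probably, or related to the research protocol, will trigger an immediate suspension of the research". The DSMB meets before the start and again "after 30% of the participants complete 14 days of the intervention". Further detail is referred to Appendix F, which is not in the supplied text.

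On the outcome side, Section 1.5 says: "We aim to recruit 10 patients with hyperphagia". It gives no power calculation. Section 1.3 D places the primary outcome, gut microbiota composition, at Weeks 0 and 4. Section 6.1 compares those two weeks, using paired tests for continuous variables, and names no analysis population, missing-data method or replacement rule.

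**The concern.** The hospitalisation rule treats two things as one: leaving the study procedures, and the end of all data collection. Section 6.3 needs them kept apart. An admission can turn out to be, or become, a life-threatening or fatal event, and the DSMB cannot apply its suspension rule without knowing how serious the event was and whether it may be related. If collection stops on admission, the protocol gives nobody the task of finding out. In a trial of 10 people, one such event could decide whether the research goes on.

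There is a second, smaller consequence. A participant removed before Week 4 has no change score, and the reason is a health event after baseline. Missing outcomes therefore depend on health during the study, and the analysis section does not say how they will be handled or reported.

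**Working it through.** **1. What the suspension rule needs, set against what the text provides.** The documents give no figure to reproduce here, so the check is a comparison of sections.

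| Needed under Section 6.3 B | At admission | After removal |
|---|---|---|
| That a serious event occurred | The subject is to contact the PI | Not applicable |
| Whether it is life-threatening or fatal | Possibly known at that contact | No collection stated |
| Whether it is at least possibly related | PI assessment under Section 4.7 E | No collection stated |
| Course and outcome | Not yet known | No collection stated |

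The adverse event paragraph in Section 4.7 E asks about severity and frequency. It mentions neither follow-up to outcome nor follow-up after removal. The notice itself depends on the subject, although Section 4.5 D expects patients with PWS to lack decision-making capacity.

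**2. When the DSMB looks.** 30% of 10 is 0.30 × 10 = 3 participants. No later meeting is stated in the supplied text, so from then on the event-triggered suspension rule is the main study-level safeguard described. A participant removed before day 14 has not completed 14 days and cannot be one of the 3 who trigger the meeting.

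**3. Missing Week 4 data.** One removal before Week 4 loses 1/10 = 10% of the pairs. The documents give no admission rate, so the risk p over the 28 days is assumed, the same for each person and independent between persons.

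- At least one of 10: 1 − (1 − p)^10
- Two or more of 10: 1 − (1 − p)^10 − 10p(1 − p)^9

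| Assumed p | At least one | Two or more |
|---|---|---|
| 2% | 18.3% | 1.6% |
| 5% | 40.1% | 8.6% |
| 10% | 65.1% | 26.4% |

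**4. Possible bias in a continuous outcome.** With k of 10 removed, the completers' mean change differs from the mean change of all 10 by (k/10) × (completers' mean − removed participants' mean). If the gap is 0.5 to 2 SD in size (assumed), the shift is 0.05 to 0.20 SD for k = 1 and 0.10 to 0.40 SD for k = 2. Its sign is the sign of the gap, which the documents do not give. The formula does not carry over to the primary outcome, which is compared through UniFrac distances with PERMANOVA.

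**The case against.** The best defence is that the hospitalisation rule concerns study measurements: stool, blood, scans and questionnaires. Adverse events have their own paragraph, Section 6.3 B covers any serious event without excluding removed participants, and the PI must be told of an admission. Some life-threatening events will be recognisable at that first contact, and the suspension rule asks only for possible relatedness. Appendix F may also contain follow-up rules. This has weight. A reader might infer that the protocol definitely ends safety follow-up or loses the event altogether, and the text does not establish either. What stands is that the rule says all data, makes no exception, and no supplied section says that follow-up survives removal. If Appendix F requires follow-up, the hospitalisation rule still contradicts it.

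Stopping research procedures on admission is also defensible. Hospital diet or antibiotics could alter a Week 4 stool sample so that it no longer reflects the fibre product, and Section 4.1 B already excludes recent antibiotic use. Whether such a sample belongs in the main analysis is a choice of estimand, and the documents do not settle it. This objection stands, and for that reason no change to the main analysis is asked for.

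**Conclusion.** The conflict between the hospitalisation rule and Section 6.3 holds on the wording supplied, and the passages should be reconciled. Its consequence is conditional: followed literally, the rule can leave the outcome and relatedness of an admission unrecorded. The safety point needs no admission rate. The conclusion assumes that Appendix F does not already resolve the matter.

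The missing-data point holds in a limited form. Removal for hospitalisation makes missing Week 4 data depend on health, at 10% of the sample per case, with bias of unknown direction. The 18% to 65% range rests wholly on the assumed 2% to 10% risk.

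Three stronger readings are not supported:

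- **That removal favours the product.** The primary outcome has no better or worse direction under PERMANOVA, and an admission could move weight, intake or microbiota either way.
- **That data are discarded.** The rule stops further collection; it does not say that data already collected are deleted.
- **That lost power is the issue.** Section 1.5 claims no power for this pilot.

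**What to change.** Check Appendix F, then reconcile Sections 4.7 E, 6.3 A and 6.3 B so that they say the same thing:

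- Hospitalisation ends study procedures but not the collection of safety data.
- The admission is reported as a serious adverse event.
- Its course is followed until outcome and relatedness are recorded, and both are sent to the DSMB.
- A named study role is responsible for obtaining this information, so that it does not rest on the subject's call alone. The consent and record-review wording in Section 5.1 should be checked to confirm that it covers this.

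In Section 6.1, commit to reporting the number removed for hospitalisation, with the reasons. Collecting Week 4 data from such participants, with the agreement of participant and guardian, would be optional; any such data would be used only in a sensitivity analysis.

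The cost is protocol wording and a few follow-up contacts per admission. Decisions about treatment are not addressed here.
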